### 1.3 Sample Size

Recent reports of COVID-19 in long-term care facilities in the United States have suggested a high rate of transmission of the SARS-CoV-2 virus, but infection control procedures may significantly decrease transmission (McMichael et al. 2020, Kimball et al. 2020). A recent study of 264 elderly volunteers ( $\geq 65$  years of age) reported 1.6 respiratory tract infections (not laboratory-confirmed) per person-year indicating approximately a 20% probability of respiratory tract infection over a given 6-week period (Mannick et. al, 2018). Infection control procedures in place during the period covered by this clinical trial are also expected to reduce the transmission of other respiratory viruses.

For purposes of calculating sample size, we assume that the proportion of subjects experiencing COVID-19 over a 6-week period is 5%, the proportion of subjects experiencing any VRI is 10%, and that effective prophylaxis will reduce the rate of COVID-19 and other VRIs by 80%.

A Cochran-Mantel-Haenszel (CMH) chi-square test stratifying by 20 LTCFs will have 87.1% statistical power to detect the difference between 5% and 1% rates of occurrence of COVID-19 across all strata at a two-sided alpha of 0.047 with a total sample size of 800, allocated equally to strata (LTCFs) and treatment groups within strata. The statistical

power remains >87% when the number of LTCFs is 5, 10, 16 or 20. The CMH chi-square test has 91% power to detect the difference between 10% and 2% rates of occurrence of VRIs over all strata at a two-sided alpha of 0.001 with 800 subjects allocated equally to 20 LTCFs. Both tests are insensitive to stratum size. Varying the number of subjects per stratum (LTCF) between a minimum of 8 to a maximum of 80 while holding both the effect size and total sample constant results in changes in the third significant figure of the test's power.

A sample size of 800 subjects (400 per treatment group) was selected.

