#### 2.2.2 Subgroup Definitions

Safety analyses will be grouped by treatment received. The primary efficacy analysis will be grouped by sex (male/female), age (65 to 79 years, 80 years and over), and race (white/non-white).

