## 4.2 Efficacy Analysis

### 4.2.1 Primary Efficacy Variables

The study has two primary efficacy endpoints: reduction in symptomatic COVID-19 disease and reduction in all VRI. The study-wise  $\alpha$  level is set at 0.05, allocated with 0.049 to the COVID-19 endpoint and 0.001 to the all VRI endpoint. See Section 2.4 for details on how the study- wise  $\alpha$  level will be allocated to the interim and final analyses. For each endpoint, the following hypotheses will be tested

$$H_0: p_1 = p_2$$

$$H_1: p_1 \neq p_2,$$

here,  $p_1$  represents the probability of symptomatic disease (either COVID-19 or VRI) in the NTZ treatment group and  $p_2$  represents the probability of symptomatic disease in the placebo group.

The proportion of subjects experiencing symptomatic COVID-19 disease in the NTZ treatment group will be compared to the similar proportion in the placebo group using a two-sided CMH test with continuity correction at  $\alpha=0.047$ . The test will be stratified by LTCF. The contingency tables will be provided with rates relative to the treatment margins. A 95% confidence interval for the odds ratio of symptomatic COVID-19 infection in the NTZ group relative to the placebo group will be provided. The risk difference for the treatment groups and a 95% confidence interval for the difference will be provided.

The proportion of subjects experiencing symptomatic VRI infections in the NTZ treatment group will be compared to the similar proportion in the placebo group using a two-sided CMH test, stratified by LTCF with continuity correction at  $\alpha=0.001$ . The contingency tables will be provided with rates relative to the treatment margins. A 95% confidence interval for the odds ratio of symptomatic VRI in the NTZ group relative to the placebo group will be provided. The risk difference for the treatment groups and a 95% confidence interval for the difference will be provided.

CMH analyses of symptomatic COVID-19 disease and symptomatic VRI will be repeated with subjects divided by sex (female or male), age (65- to 79 years or 80 years and over), and race (white or non-white). Estimates and confidence intervals for the odds ratio and relative risk differences will be provided.

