## 8.0 List of Analysis Tables, Figures and Listings

Table No.	Table Title
14.1.1.1	Subject Disposition Summary by Treatment and Overall (All Subjects)
14.1.2.1	Summary of Major Protocol Deviations (Safety Population)
14.1.2.2	Summary of Minor Protocol Deviations (Safety Population)
14.1.3.1	Summary of Demographic Categorical Variables by Treatment and Stratum (Safety Population)
14.1.3.2	Summary of Demographic Quantitative Variables by Treatment and Stratum (Safety Population)
14.1.4	Summary of Treatment Compliance (Safety Population)
14.2.1.1	Cochran-Mantel-Haenszel Test Results: Symptomatic COVID-19 Subject Status (ITT Population)
14.2.1.2	Cochran-Mantel-Haenszel Test Results: Symptomatic VRI Subject Status (ITT Population)
14.2.1.3	Cochran-Mantel-Haenszel Test Results: Symptomatic COVID-19 Subject Status with Best-Case and Worst-Case Analysis of Missing Data (ITT Population)
14.2.1.4	Cochran-Mantel-Haenszel Test Results: Symptomatic VRI Subject Status with Best-Case and Worst-Case Analysis of Missing Data (ITT Population)
14.2.1.5	Cochran-Mantel-Haenszel Test Results: Symptomatic COVID-19 Subject Status with Tipping Point Analysis of Missing Data (ITT Population)
14.2.1.6	Cochran-Mantel-Haenszel Test Results: Symptomatic VRI Subject Status with Best-Tipping Point Analysis of Missing Data (ITT Population)
14.2.1.7	Cochran-Mantel-Haenszel Test Results by Sex: Symptomatic COVID-19 Subject Status (ITT Population)
14.2.1.8	Cochran-Mantel-Haenszel Test Results by Sex: Symptomatic VRI Subject Status (ITT Population)
14.2.1.9	Cochran-Mantel-Haenszel Test Results by Age Group: Symptomatic COVID-19 Subject Status (ITT Population)
14.2.1.10	Cochran-Mantel-Haenszel Test Results by Age Group: Symptomatic VRI Subject Status (ITT Population)
14.2.1.11	Cochran-Mantel-Haenszel Test Results by Race: Symptomatic COVID-19 Subject Status (ITT Population)
14.2.1.12	Cochran-Mantel-Haenszel Test Results by Race: Symptomatic VRI Subject Status (ITT Population)
14.2.2.1	Cochran-Mantel-Haenszel Test Results: COVID-19 Related Hospitalization Status (ITT Population)

Table No.	Table Title
14.2.2.2	Cochran-Mantel-Haenszel Test Results: COVID-19 Related Mortality Subject Status (ITT Population)
14.2.2.3	Cochran-Mantel-Haenszel Test Results: COVID-19 Antibody Test Subject Status (ITT Population)
14.2.3.1	Cochran-Mantel-Haenszel Test Results: VRI Related Hospitalization Subject Status (ITT Population)

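### The SAP repeats the CMH test within each sex, age and race level but never compares the levels, so at the planned COVID-19 effect a uniform benefit would be significant in only one level in about half of trials or more

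*SAP*

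**What the plan says.** SAP 2.2.2 lists the groupings and nothing more: "The primary efficacy analysis will be grouped by sex (male/female), age (65 to 79 years, 80 years and over), and race (white/non-white". SAP 4.2.1 supplies the method: "CMH analyses of symptomatic COVID-19 disease and symptomatic VRI will be repeated with subjects divided by sex (female or male", then "age (65- to 79 years or 80 years and over), and race (white or non-white". The next sentence adds "Estimates and confidence intervals for the odds ratio and relative risk differences will be provided", which I read as odds ratios and risk differences, as for the primary analysis. The primary COVID-19 comparison is made "using a two-sided CMH test with continuity correction at" 0.047, and the VRI comparison at 0.001.

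SAP 8.0 gives the subgroups six tables, 14.2.1.7 to 14.2.1.12. The first is titled "Cochran-Mantel-Haenszel Test Results by Sex: Symptomatic COVID-19 Subject Status (ITT Population", and the other five follow the same pattern. Three factors, two levels and two endpoints make 3 × 2 × 2 = 12 within-level tests.

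Neither document names an interaction term, a test of homogeneity, a significance level for subgroups or a rule for reading differences between levels. Protocol 8.4.1 plans no subgroup analysis and leaves other analyses to the SAP.

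**The concern.** The purpose of a subgroup analysis is to ask whether the treatment effect differs between levels. Two separate tests do not answer that. Each asks whether the effect in its own level can be told from zero, and the answer depends heavily on how many events the level holds. With a modest event count, one result below the threshold and one above it is an ordinary outcome even when the drug works equally well in both.

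The SAP expects only 24 COVID-19 events in the whole trial. The six tables are titled as test results, so the p-values will be prominent. A reader could conclude that NTZ protects one kind of resident and not another from a pattern that chance produces routinely, and no planned output would correct that reading.

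**Working it through.** **Inputs.** From SAP 1.3: COVID-19 5% versus 1%, VRI 10% versus 2%, 400 per arm, 20 LTCFs of 40 subjects, two-sided alphas 0.047 and 0.001. From SAP 4.2.1: CMH with continuity correction, stratified by LTCF. Assumed: subgroup splits of 50:50 to 80:20, and each endpoint's own alpha carried into its subgroups, because the analyses are described as repeated.

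**1. Reproduce the plan's power.** With n per arm, d the rate difference and p̄ the mean rate, power = Φ((d − 1/n − z·se0)/se1), where se0 = √(2p̄(1−p̄)/n) and se1 = √((p0(1−p0)+p1(1−p1))/n).

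For COVID-19, n = 400: se0 = 0.01206, se1 = 0.01198, z = 1.986. Then (0.04 − 0.0025 − 1.986 × 0.01206)/0.01198 = 1.13, and Φ(1.13) = 87.1%. The SAP says the test "will have 87.1% statistical power to detect the difference between 5% and 1% rates of occurrence of" COVID-19. The same formula gives 91.0% for VRI, against 91% stated.

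**2. Power within a level at an even split.** Here n = 200 per arm: se0 = 0.01706, se1 = 0.01694. Then (0.04 − 0.005 − 1.986 × 0.01706)/0.01694 = 0.066, and Φ(0.066) = 52.6%.

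**3. Disagreement under a uniform effect.** If the two levels have powers a and b, the chance that exactly one is significant is a(1−b) + b(1−a).

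- 50:50: 2 × 0.526 × 0.474 = 50%.
- 70:30: 0.707 × 0.710 + 0.290 × 0.293 = 59%.
- 80:20: 0.774 × 0.835 + 0.165 × 0.226 = 68%.

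**4. Simulation of the stratified test itself** (20 LTCFs, same true rates in both levels; its overall power is about 90%). The normal approximation overstates power in the smaller level, so the simulated disagreement is higher for uneven splits.

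| Split | COVID-19 power, larger / smaller level | Exactly one significant |
|---|---|---|
| 50:50 | 53% / 53% | 50% |
| 60:40 | 64% / 38% | 54% |
| 70:30 | 74% / 23% | 63% |
| 80:20 | 81% / 9% | 76% |

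With 5 LTCFs the results are nearly the same. Using 0.049, the alpha that applies if no interim efficacy review takes place, leaves the closed-form even-split figure at 50%.

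Why the small level fails: 20% of 24 events is about 5. If all 5 fell on placebo, in different facilities with balanced arms, the statistic would be (2.5 − 0.5)²/1.25 = 3.2, p = 0.07. A 5–0 result would be reported as not significant.

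**5. Sensitivity.**

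- COVID-19 with a true 60% reduction: 37% at 50:50, rising to about 45% at 80:20. With a 50% reduction: about 27% to 30%.
- COVID-19 among trials with a significant overall result: 54% at 50:50 for the planned effect, and 58% for a 60% reduction.
- COVID-19 without continuity correction: 45% at 50:50.
- VRI, planned effect, alpha 0.001: 49% at 50:50, 69% at 70:30, 82% at 80:20.
- VRI, planned effect, read at 0.05: 17%, 37% and 63% for the same splits.

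**6. Direct comparison.** I took a Wald test on the difference of the two log odds ratios (0.5 added to each cell, two-sided 0.05, LTCF ignored). Under the same uniform effect it flags a difference in about 1% to 2% of trials for COVID-19 and 2% to 3% for VRI.

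Its power is low. With an 80% COVID-19 reduction in one level and none in the other, it rejects in about 36% of trials at 50:50. When the effect is missing from the smaller level at 80:20, it rejects in about 37%, and splits in between reach no more than about 42%.

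**The case against.** The best defence is that the SAP already plans an estimate and interval for each level, which is the most useful part of subgroup reporting, and that it sets no rule by which a subgroup claim would be made. Both points stand. A reader might infer that the SAP judges subgroups by their p-values, but it does not say so. What remains is that none of the planned output contrasts the levels, while all six tables are headed as tests.

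Second, the frequencies are conditional. They use the planned 80% reduction, an alpha the SAP does not assign to subgroups, and splits the documents do not give. This also stands, and the sensitivity figures show how far the result moves. The age factor fits least well. Protocol 4.1 admits residents from age 55, while the SAP age bands start at 65, so subjects aged 55 to 64 belong to neither band and the two-level calculation describes age only approximately.

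Third, an interaction test would itself be weak, and its low false-flag rate is not evidence that it can detect a real difference. That is correct and limits what the fix can deliver.

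Finally, the subgroups are supportive and no primary conclusion depends on them. This bears on priority, but the omission remains.

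**Conclusion.** The concern holds in a bounded form. The plan tests within levels, provides nothing that compares them, and leaves the subgroup alpha open. If the planned COVID-19 effect is uniform and the primary alpha carries over, exactly one level is significant in about 50% of trials at an even split and about 76% at 80:20. A smaller true effect brings this down to about 37% to 45% (60% reduction). For VRI the result depends on the unstated alpha: about 49% at 0.001 and 17% at 0.05, both at an even split.

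Three stronger readings are not supported:

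- That disagreement occurs in at least half of trials whatever the effect. The sensitivity results contradict this.
- That NTZ will appear to fail in men, the oldest residents or non-white residents. At an even split either level is equally likely to be the non-significant one. At uneven splits it is normally the smaller level, and the documents do not say which that is.
- That every level is too small to test. A level with 70% to 80% of subjects would have 74% to 81% power for COVID-19.

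This is an inexpensive improvement to the SAP that should be made. It does not threaten the primary analysis.

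**What to change.** In SAP 4.2.1 and Tables 14.2.1.7 to 14.2.1.12:

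- Present the already planned odds ratio and risk difference, with intervals, for each level as the main subgroup output.
- Add one treatment-by-subgroup test per factor and endpoint, stating its scale, its nominal alpha and how LTCF is handled. With few events, a penalised (Firth) logistic interaction term or a Mantel-Haenszel heterogeneity test would be suitable. The 1% to 3% false-flag rate above was obtained with a simple Wald contrast, so the chosen method should be checked by simulation.
- State that any within-level p-values are descriptive and are not evidence that the effect differs between levels.
- State that the interaction test has low power, so that a non-significant result does not show equal effects.
- While this paragraph is open, reconcile the SAP age bands with the protocol's enrolment age.

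The cost is a few lines of text and three further tests per endpoint, six in all, on data already collected. The sponsor gives up within-level p-values as a basis for subgroup claims. The gain is protection against false claims; the trial will still have little ability to detect a real difference between levels.

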### 4.2.2 Secondary Efficacy Variables

The proportion of subjects in the NTZ and placebo groups experiencing hospitalization due to COVID-19 or its complications will be analyzed using a CMH test stratified by LTCF

with appropriate continuity correction at an unadjusted  $\alpha=0.05$ . The contingency tables will be provided with rates relative to the treatment margins.

The mortality rate due to COVID-19 or complications in the two treatment groups will be compared using a CMH test stratified by LTCF with continuity correction at unadjusted  $\alpha=0.05$ . Contingency tables with rates computed relative to the treatment margins will be provided.

The proportion of subjects in the treatment groups testing positive for SARS-CoV-2 antibodies at either Week 6 or Week 8 will be compared using a CMH test stratified by LTCF. The contingency tables will be provided with rates computed relative to the treatment margins.

#### **4.2.3 Exploratory Efficacy Variables**

Hospitalization due to VRI or complication thereof, mortality due to VRI or complications thereof, Presence of an ARI, hospitalization due to ARI or complications thereof, and mortality due to ARI or complications thereof will each be summarized in a three-way contingency table (Stratum\*Treatment\*Variable) with counts and percentages relative to the table row (i.e., treatment) margins. A CMH test stratifying by LTCF will be provided for each variable.

### **5.0 Analysis of Safety**

#### **5.1 Description of Safety Variables**

The safety analysis variables are defined as follows:

- Adverse Events (AEs)
- Clinical Laboratory Values (Hematology, Blood Chemistry, and Urinalysis)
- Physical Exam
- Vital Signs

The following describes the safety analyses to be performed for the study. All safety analyses will be performed on the safety population.

#### **5.2 Description of Safety Analyses**

##### **Adverse Events**

Adverse events will be graded by the investigator according to the “Guidance for Industry: Toxicity Grading Scale for Healthy Adult and Adolescent Volunteers Enrolled in Preventive Vaccine Trials” (FDA/CDER, 2007) as adapted in the Study Protocol. The investigator will also assess causality (relationship to treatment) as *Definitely related*, *Probably related*, *Possibly related*, and *Unrelated*. AEs will be coded using the Medical Dictionary for Regulatory Activities version 23.0 or higher (MedDRA®). Treatment-

emergent AEs (TEAEs), defined as any AE that occurs after a patient receives the first dose of the assigned study treatment, will be summarized by the number and proportion of patients reporting at least one occurrence of the AE. Frequencies and rates of each TEAE will be summarized by MedDRA preferred term within system organ class (SOC), by severity grade, and relation to treatment for each treatment group. The rate calculation will be based on the number of patients in the safety population for the relevant treatment group.

Treatment emergent serious adverse events (TESAEs) will be summarized and displayed by frequency and rate by MedDRA preferred term within SOC.

A by-patient AE data listing of all adverse events including verbatim term, coded term, grade, and relation to treatment will be provided.

### **Laboratory Tests**

Clinical laboratory tests will be performed at the times prescribed in the protocol. The following clinical laboratory tests will be performed:

#### **Hematology:**

Hemoglobin, hematocrit, complete white blood count (total and differential), platelet count, random blood glucose, total cholesterol, HDL, LDL, and triglycerides.

#### **Clinical Chemistry:**

AST, ALT, GGT, alkaline phosphatase, bilirubin (total and direct), BUN, creatinine, sodium, potassium, and chloride.

#### **Urinalysis:**

Appearance, glucose, protein, and blood.

Clinical laboratory results and the change from baseline (CFB, baseline defined as the value at the baseline visit) will be summarized for the safety population with summary statistics (mean, standard deviation, n, minimum, median, maximum) by time point for each treatment group. Clinical laboratory results will be classified as "Normal", or "Abnormal"; "Abnormal" results will be further classified by the PI as "Clinically significant" (CS) or "Not clinically significant" (NCS). Clinical laboratory results will be summarized by a shift table from baseline with categories "Normal", "Abnormal (NCS)", and "Abnormal (CS)". Urinalysis appearance results will appear only in the shift table.

All clinically significant abnormal laboratory findings will be reported as AEs. All AEs recorded will be listed.

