10. ADVERSE EVENTS

The term “adverse event” is defined for purposes of this study as any unwanted physical, psychological or behavioral change experienced by a subject during the course of the study and after taking the first dose of study medication regardless of its severity or relation to the study. Adverse events may include symptoms, signs, unexpected worsening of pre-existing conditions, clinically significant changes in laboratory values, diseases and syndromes, and significant and unexpected failures of pharmacological action of other medications. Symptoms of VRIs (cough, sore throat, nasal obstruction, fatigue, headache, myalgia, feverishness) and complications of VRIs will not be reported as adverse events.

Adverse events will be recorded on the appropriate EDC forms throughout the study, and the severity of each adverse event will be graded on a four-point scale: mild, moderate, severe, or life-threatening (See [Appendix II](#)). The duration of the adverse event and relationship to the study drug will also be recorded. All adverse events must be followed until their resolution or stabilization even beyond the planned study period.

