11. DISCONTINUATION

11.1. Study Discontinuation

The study may be discontinued under the following circumstances:

1. The Sponsor reserves the right to discontinue the study at any time.
2. Adverse event listings will be produced for safety monitoring at least once every two weeks during recruitment. The data will be tested to determine if there are greater than 20% of the subjects who have had \geq Grade 3 adverse events considered by the Investigator to be possibly, probably or definitely related to the study drug (defined by the Toxicity Grading Scale Tables provided in [Appendix II](#)).

If greater than 20% of the subjects have at least one Grade 3 or Grade 4 adverse event considered to be possibly, probably or definitely related to the study drug by the study Medical Monitor, then the study must be stopped and the Institutional Review Boards, and FDA's Division of Anti-Infectives will be notified. All safety and activity data will be submitted to the FDA in a timely manner.

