### **Physical Exam**

Physical exams will be performed as outlined in the protocol. All clinically significant abnormal PE findings will be recorded as AEs. All physical exam data will be listed as shown in Appendix B.

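### SAP 5.2 reports all clinically significant abnormal findings as AEs, while Protocol 10 requires a change, so a stable pre-dose abnormality can be tabulated as treatment-emergent

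*SAP*

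**What the plan says.** **SAP 5.2, laboratory tests.** Abnormal "results will be further classified by the PI as" clinically significant or not, and then: "All clinically significant abnormal laboratory findings will be reported as AEs". Neither sentence mentions the baseline value. The same section also plans change-from-baseline statistics and a shift table in which clinically significant abnormality is one of the categories.

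**SAP 5.2, physical exam.** "All clinically significant abnormal PE findings will be recorded as AEs".

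**SAP 5.2, adverse events.** A TEAE is "defined as any AE that occurs after a patient receives the first dose of the assigned study treatment". There is no clause on worsening. The SAP has no AE definition of its own.

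**Protocol 10.** An AE is "any unwanted physical, psychological or behavioral change experienced by a subject during the course of the study and after taking the first dose". Its examples include "unexpected worsening of pre-existing conditions, clinically significant changes in laboratory values".

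**Protocol 11.1.** The stopping condition begins "If greater than 20% of the subjects have at least one Grade 3 or Grade 4 adverse event" and then requires that the event be judged possibly, probably or definitely related to study drug.

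**The concern.** The two documents give different answers for the same laboratory result. Protocol 10 asks whether something changed after dosing. The SAP sentence asks only whether the result is abnormal and clinically significant. A site or programmer who follows the SAP sentence will report findings that the protocol would not call adverse events.

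The case is foreseeable. The SAP's shift table provides for residents who are already abnormal and clinically significant at baseline. No exclusion criterion in Protocol 4.2 concerns laboratory values. Apart from hemoglobin, which also has change-from-baseline rows, Appendix II does not grade laboratory values by change from the subject's own baseline; most have absolute cut-offs or multiples of the normal limit.

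At stake is how readable the TEAE tables are. These are the tables that carry severity grade and relationship to treatment. Background findings would add similar numbers to both arms and make a real difference in laboratory-related events look proportionally smaller.

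**Working it through.** The plan states no figure on this point, so there is nothing to reproduce. The check has two parts: one case taken through both documents, then an illustration of size on stated assumptions.

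**1. One case under both texts.** Take a resident with creatinine 2.3 mg/dL before dosing and 2.3 mg/dL at Week 3, judged clinically significant by the investigator.

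| Rule | Result |
|---|---|
| Protocol 10 (change or worsening needed) | Not an AE |
| SAP 5.2 laboratory sentence (clinically significant abnormality suffices) | AE |
| SAP TEAE definition, onset recorded before the first dose | Not a TEAE |
| SAP TEAE definition, first recorded as an AE at Week 3 | TEAE |
| Appendix II, Table 13 (creatinine 2.1 to 2.5) | Grade 3 as a guideline |

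SAP Table 2 adds a second route. A completely missing AE onset date is set to the date of first dose. So is an onset with the month missing when the year is that of first dose.

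**2. Effect on a TEAE row or total.** Let p be the true new-event rate and b the share of each arm with a counted pre-existing finding, independent of new events. The observed rate is p' = 1 − (1 − p)(1 − b), so the risk difference is multiplied by (1 − b). Both the new-event rates (6% and 3%) and b are assumptions; the documents give neither.

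| b | Observed rates | Risk difference (points) | Risk ratio |
|---|---|---|---|
| 0% | 6.0% v 3.0% | 3.0 | 2.00 |
| 10% | 15.4% v 12.7% | 2.7 | 1.21 |
| 20% | 24.8% v 22.4% | 2.4 | 1.11 |
| 30% | 34.2% v 32.1% | 2.1 | 1.07 |
| 50% | 53.0% v 51.5% | 1.5 | 1.03 |

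For example, at b = 10%: 1 − 0.94 × 0.90 = 0.154 and 1 − 0.97 × 0.90 = 0.127. The ratio falls quickly and the difference slowly.

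**3. Effect on the Protocol 11.1 count.** Let r be the share with a genuine related Grade 3 or 4 event, b now the share with a pre-existing Grade 3 or 4 finding, and q the proportion of those findings judged related. The counted share is r + (1 − r)·b·q. Assume r = 2%. To exceed 20% (at least 161 of 800, if all 800 form the denominator), q must exceed 0.18 / (0.98·b):

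- b = 10%: not reachable. Even q = 100% gives 0.02 + 0.98 × 0.10 = 11.8%.
- b = 20%: q above about 92%.
- b = 30%: q above about 61%.
- b = 50%: q above about 37%.

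If no pre-existing finding is judged related (q = 0), the contribution is zero for any b.

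**The case against.** The strongest reply is that investigators record AEs under the protocol, and Protocol 10 already demands change. On that view the SAP sentence is loose drafting that Protocol 10 overrides. This limits the point: a reader might infer that the plan has no change requirement at all, and that is not so. But the SAP sentence is a positive rule covering all such findings, and neither document says which rule governs.

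Other parts of the reply also stand:

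- A reader might infer that pre-existing disease automatically counts as treatment-emergent. It does not. A finding with a recorded pre-dose onset falls outside the TEAE definition. Clinical significance is the investigator's judgement, and Appendix II calls its laboratory limits guidelines that depend on institutional norms.
- A reader might infer a loss of statistical power. Protocol 8.4.3 makes safety descriptive, so there is no test to lose power.
- Dilution is local. The SAP tabulates by preferred term within system organ class, so a chronic creatinine elevation cannot dilute a diarrhea row. The shift and change-from-baseline tables compare laboratory effects directly.
- The examination rule matters less, because the protocol's post-baseline examinations are already performed as warranted for change from baseline.
- A reader might infer that background findings would drive the stopping count. Entry needs Grade 3 or 4 and a relatedness judgement, and a stable pre-dose abnormality fits the unrelated category well. Relatedness is not a complete filter, since the possibly-related category allows an alternative cause and assessors must assume active drug. Even so, step 3 shows that crossing the limit needs a high background share and frequent attribution to drug.

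**Conclusion.** The inconsistency is real. SAP 5.2 is broader than Protocol 10 for laboratory findings and, less importantly, for examination findings, and the TEAE definition does not close the gap. Read literally, the SAP can place a stable pre-dose abnormality, first recorded after dosing, in the laboratory-related TEAE rows and the overall TEAE totals of both arms.

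The direction is clear but the size is not, because it depends on a baseline prevalence that the documents do not give. On the assumed rates, and with background findings independent of new events, 10% to 20% background leaves a risk difference of 2.7 to 2.4 points out of 3.0 and a ratio of 1.21 to 1.11 instead of 2.00. The documents do not support a claim that the safety comparison as a whole is compromised or that the stopping rule would be triggered by background disease. This is a modest correction to definitions that leaves the efficacy analysis untouched.

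**What to change.** Align the three SAP 5.2 statements with Protocol 10:

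- Report clinically significant laboratory or examination findings as AEs when they are new, or show clinically significant worsening, compared with the pre-dose value.
- Define a TEAE as an AE that is new or worsened after the first dose.
- Keep unchanged abnormalities in the shift tables and listings.

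The criterion should not be limited to a worse grade. In Appendix II, BUN above 31 mg/dL is Grade 3 and the next grade is reached only when dialysis is required, so a large rise within Grade 3 would be lost although Protocol 10 could count it as a clinically significant change.

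The sponsor should also reconcile which AE definition feeds the Protocol 11.1 count. No change to that rule is proposed here.

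The cost is SAP wording and a comparison in the programming. Protocol 5.2 lists the baseline blood sample ahead of the first dose, and Protocol 5.1 supplies the pre-dose examination at screening. The downside is that investigators and programmers must compare each finding with its pre-dose value, which Protocol 10 already implies.
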